6.4. Study Intervention Compliance

The infusion of study intervention into participants will be under the supervision of the Investigator or their designee to ensure that participants receive the appropriate dose at the appropriate time points during the study.

The date and time of each dose administered in the clinic will be recorded in the source documents and case report form (CRF).

The volume (mL) of study intervention and study participant identification will be confirmed at the time of dosing by a member of the study site staff other than the person administering the study intervention.

For additional information on study intervention and management, refer to the Pharmacy Manual

6.5. Concomitant Therapy

Any medication (including over the counter or prescription medicines, vitamins, and/or herbal supplements), vaccine, or other specific categories of interest that the participant is receiving at the time of enrollment or receives during the study must be recorded along with:

- Reason for use
- Dates of administration, including start and end dates
- Dosage information including dose and frequency

The Alexion Medical Monitor or designee should be contacted if there are any questions regarding concomitant or prior therapy.

6.5.1. Allowed Medicine and Therapy

6.5.1.1. Dermatomyositis Treatment

Participants should not discontinue an effective therapy solely for the purpose of entering the clinical study.

Participants who continue allowed DM treatments as concomitant therapy will be required to have received those treatments for at least the amount of time described in Table 14 before the Day 1 Visit and will be required to remain on the same stable dose during the Randomized

Controlled Period. Maximally allowed stable doses are described in Table 14. In some cases, stable doses of allowed DM treatments may be decreased due to safety and/or tolerability issues. Investigators must contact the Alexion Medical Monitor or designee to discuss possible dose changes before adjusting the participant's allowed DM treatment dose.

During the OLE Period, doses of allowed DM treatments may be changed or discontinued. New allowed DM treatments may be started in the OLE Period. Medications listed in Section 6.5.2 are prohibited during the OLE Period. Any change in medication will be properly documented in the CRF.

Table 14: Allowed Concomitant DM Treatments

| Medication | Duration of Stable Dose Before Day 1 Visit | Treatment Duration Required Before Day 1 Visit | Maximally Allowed Stable Dose as Concomitant therapy | Dose Modifications Permitted During Randomized Controlled Period ^a |
|---|--|--|--|---|
| Azathioprine | 4 weeks | 12 weeks | 2.5 mg/kg daily | None |
| Cyclosporine | 4 weeks | 12 weeks | 5 mg/kg daily | None |
| Glucocorticoid | 4 weeks | 4 weeks | 20 mg daily Prednisone equivalent ^b | None |
| Hydroxychloroquine | 4 weeks | 12 weeks | 400 mg daily | None |
| Intramuscular glucocorticoids ^{b,c} | NA | NA | 80 mg per dose | Only 2 injections allowed (must be separate days) |
| Leflunomide | 4 weeks | 12 weeks | 20 mg daily | None |
| Methotrexate | 4 weeks | 12 weeks | 25 mg/week | None |
| Mycophenolate mofetil/mycophenolic acid | 4 weeks | 12 weeks | 3000 mg daily | None |
| Sulfasalazine | 4 weeks | 12 weeks | 3 g daily | None |
| Tacrolimus | 4 weeks | 12 weeks | 0.2 mg/kg daily | None |

^a Unless medically necessary or due to participant safety reasons.

Abbreviations: DM = dermatomyositis; NA = not applicable

Alternatively, participants may choose to discontinue previous DM treatments before the Day 1 Visit but will be required to complete an appropriate washout period, as described in Table 15.

Table 15: Washout Periods Required Before Day 1 Visit

| Medication ^a | Washout |
|-------------------------|---------|
| Azathioprine | 4 weeks |

^b Prednisone equivalent medications and doses are described in the Study Manual.

^c Do not administer within 72 hours prior to a study visit.

Table 15: Washout Periods Required Before Day 1 Visit

| Medication ^a | Washout |
|---|----------|
| Cyclosporine | 4 weeks |
| Glucocorticoid b | 4 weeks |
| Hydroxychloroquine | 8 weeks |
| Intramuscular glucocorticoids | 4 weeks |
| Leflunomide | 12 weeks |
| Methotrexate | 4 weeks |
| Mycophenolate mofetil/mycophenolic acid | 4 weeks |
| Sulfasalazine | 4 weeks |
| Tacrolimus | 4 weeks |

^a For questions regarding a washout period for previous dermatomyositis treatments not listed please consult the Alexion Medical Monitor or designee.

6.5.1.2. Other Allowed Therapies

- Medications listed below may be taken as needed but should not be administered within 72 hours prior to the study visit.
 - Antihistamines
 - Non-steroidal anti-inflammatory drugs (NSAIDs)
 - Acetaminophen
 - o Antiprurities

However, participants taking the medications listed above at a stable dose for at least 4 weeks before Screening are allowed to continue these medications.

- Topical steroid hydrocortisone (1%) may be taken as needed but should not be administered within 72 hours prior to the study visit.
- Vitamin B12, vitamin E, creatine, coenzyme Q10, and biotin supplements are permitted
 in this study. Participants who take any or all of these supplements should be on a stable
 dose beginning 14 days prior to the first dose of study intervention and remain on the
 same stable dose for the duration of the Randomized Controlled Period unless alteration
 in dose is deemed medically necessary or reviewed with the Alexion Medical Monitor or
 designee.
- All other vitamins and supplements are permitted in this study. Participants are
 encouraged to remain on stable dosing for the duration of the Randomized Controlled
 Period of the study.

^b 8-week washout before randomization if received ≥ 1 mg/kg/day or on a maintenance dose > 20 mg/day

6.5.2. Disallowed Medicine and Therapy

The following medications and therapies are prohibited during the study:

- Treatments listed in Table 16. Participants must complete the appropriate washout period for these treatments as listed in Table 13 before the Day 1 Visit.
- Eculizumab or other complement inhibitory agent.
- Any investigational therapy or off-label usage of an approved product other than the allowed medication in this protocol for the treatment of DM during the study (Table 14).

Table 16: Washout Periods Required Before Day 1 for Prohibited Medications

| Medication ^a | Washout |
|-------------------------------------|----------|
| Abatacept | 12 weeks |
| Adalimumab | 12 weeks |
| Anakinra | 1 week |
| Corticotropin injection | 8 weeks |
| Cyclophosphamide | 12 weeks |
| Etanercept | 4 weeks |
| Infliximab | 8 weeks |
| IVIg/SCIg | 12 weeks |
| IV glucocorticoids | 4 weeks |
| Ocrelizumab | 20 weeks |
| Rituximab | 24 weeks |
| Tocilizumab | 10 weeks |
| Tofacitinib or other JAK inhibitors | 4 weeks |

^a For questions regarding a washout period for previous prohibited dermatomyositis treatments and monoclonal antibodies not listed please consult the Alexion Medical Monitor or designee.

Abbreviations: IVIg = intravenous immunoglobulin; JAK = Janus kinase; SCIg = subcutaneous immunoglobulin

Participants who require prohibited medications at any point during the study will be discontinued from the study intervention.

6.5.3. Acute Therapy with Standard DM Treatment

To allow for sufficient time for the study drug to become effective, it is recommended that participants not receive any acute therapy with standard DM treatment during the first 10 weeks of receiving the study intervention during the Randomized Controlled Period.

Acute therapy with standard DM treatment includes an increased dose of a medication that is currently being taken for DM or the initiation of a new DM treatment (glucocorticoid and/or ISTs).

Participants in the Randomized Controlled Period (Part A and Part B) who receive acute therapy with standard DM treatment with protocol allowed medication (see Section 6.5.1) upon confirmation of Clinical Worsening (see Section 4.1.3) will discontinue study intervention, complete the Randomized Controlled Period, and will be permitted to enter the OLE Period. Participants in the Randomized Controlled Period who receive acute therapy with standard DM treatment for other reasons will discontinue study intervention, complete the Randomized Controlled Period visit assessments, but will not be permitted to enter the OLE Period.

All participants who received acute therapy with standard DM treatment during the Randomized Controlled Period and are permitted to enter the OLE will require a weight-based blinded loading dose at Week 26 (Part A) or Week 50 (Part B) as described in Table 12, Table 13, and Section 6.1.1.

Participants randomized to ravulizumab:

Participants in Part A who discontinue therapy before Week 18 will resume treatment in Week 26 with the weight-based blinded loading dose described in the Placebo Group section of Table 12 (no dose adjustments needed).

Participants in Part A who discontinue therapy after Week 18 will resume treatment in Week 26 with the weight-based blinded dose described in the Ravulizumab Group section of Table 12 (no dose adjustments needed).

Participants in Part B who discontinue therapy before Week 42 will resume treatment in Week 50 with the weight-based blinded loading dose described in the Placebo Group section of Table 13 (no dose adjustments needed).

Participants in Part B who discontinue therapy after Week 42 will resume treatment in Week 50 with the weight-based blinded dose described in the Ravulizumab Group section of Table 13 (no dose adjustments needed).

Participants randomized to placebo:

Participants will resume treatment in Week 26 (Part A) or Week 50 (Part B) with the weight-based blinded loading dose described in the Placebo Group section of Table 12 and Table 13 (no dose adjustments needed).

All participants will then continue to receive the weight based open-label maintenance dose.

OLE Period

Adjustments of protocol allowed DM medications will be permitted throughout the OLE Period.

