6.1.1. Study Intervention(s) Administered

At the scheduled dosing visits (Section 1.3), study intervention infusion should be performed after all other tests and procedures have been completed, excluding the post-dose blood sampling for PK/PD.

The ravulizumab or placebo dose for each participant will be based on body weight and will be administered as an IV infusion. The dosing regimen consists of an initial loading dose at the beginning of the Randomized Controlled Period and the OLE followed by maintenance dosing initiated 2 weeks after loading dose. The maintenance dosing will be administered q8w during the Randomized Controlled Period and OLE (Table 12 and Table 13).

Refer to Table 11 for a reference chart for weight-based dosing.

Table 11: Weight-based Doses of Ravulizumab

| Body Weight Range (kg) ^a | Loading Dose (mg) | Maintenance Dose (mg) |
|--|-------------------|-----------------------|
| \geq 30 to < 40 | 1200 | 2700 |
| \geq 40 to < 60 | 2400 | 3000 |
| ≥ 60 to < 100 | 2700 | 3300 |
| ≥ 100 | 3000 | 3600 |

Note: Additional dose preparation instructions are provided in the pharmacy manual.

Abbreviation: aHUS = atypical hemolytic uremic syndrome; gMG = generalized myasthenia gravis; PNH = paroxysmal nocturnal hemoglobinuria

^a Dose regimen will be based on the last recorded study visit body weight. If the study intervention is prepared the night before a visit, the weight from the most recent study visit should be used.

Table 12: Reference Chart for Weight-based Dosing – Study Part A

| Study Period | Dosing | Body Weight (kg) ^a | Ravulizumab Dose (mg) | Ravulizumab Volume (mL) | Placebo Volume (mL) | Diluent (0.9% Sodium Chloride) Volume (mL) | Total Volume (mL) |
|---|--------------------|-------------------------------|-----------------------------|----------------------------|---------------------------|---|----------------------|
| Ravulizumab G | roup | | | | | | |
| Randomized | Loading dose | \geq 30 to < 40 | 1200 | 120 | 0 | 120 | 240 |
| Controlled (10 mg/mL | (Day 1) | ≥ 40 to < 60 | 2400 | 240 | 0 | 240 | 480 |
| formulation) | | ≥ 60 to < 100 | 2700 | 270 | 0 | 270 | 540 |
| | | ≥ 100 | 3000 | 300 | 0 | 300 | 600 |
| | Maintenance dose | ≥ 30 to < 40 | 2700 | 270 | 0 | 270 | 540 |
| (Days 15, 71, 127) | (Days 15, 71, 127) | ≥ 40 to < 60 | 3000 | 300 | 0 | 300 | 600 |
| | | \geq 60 to < 100 | 3300 | 330 | 0 | 330 | 660 |
| | ≥ 100 | 3600 | 360 | 0 | 360 | 720 | |

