| Open-Label Blinded dose | ≥ 30 to < 40 | 900 | 90 | 30 | 120 | 240 | |
| Extension (10 mg/mL | (Day 183) | ≥ 40 to < 60 | 900 | 90 | 150 | 240 | 480 |
| formulation) | | ≥ 60 to < 100 | 900 | 90 | 180 | 270 | 540 |
| | | ≥ 100 | 900 | 90 | 210 | 300 | 600 |
| Open-Label Extension (100 mg/mL formulation) Open-label maintenance dose (Days 197 to 1037, q8w) | ≥ 30 to < 40 | 2700 | 27 | 0 | 27 | 54 | |
| | ≥ 40 to < 60 | 3000 | 30 | 0 | 30 | 60 | |
| | ` • | \geq 60 to < 100 | 3300 | 33 | 0 | 33 | 66 |
| | | ≥ 100 | 3600 | 36 | 0 | 36 | 72 |

Table 12: Reference Chart for Weight-based Dosing – Study Part A

| Study Period | Dosing | Body Weight (kg) ^a | Ravulizumab Dose (mg) | Ravulizumab Volume (mL) | Placebo Volume (mL) | Diluent (0.9% Sodium Chloride) Volume (mL) | Total Volume (mL) |
|---|-----------------------|-------------------------------|-----------------------------|----------------------------|---------------------------|---|----------------------|
| Placebo Group | • | | | | | | |
| Randomized | Loading dose | ≥ 30 to < 40 | 0 | 0 | 120 | 120 | 240 |
| Controlled | (Day 1) | ≥ 40 to < 60 | 0 | 0 | 240 | 240 | 480 |
| (10 mg/mL formulation) | | \geq 60 to < 100 | 0 | 0 | 270 | 270 | 540 |
| | | ≥ 100 | 0 | 0 | 300 | 300 | 600 |
| | Maintenance dose | \geq 30 to < 40 | 0 | 0 | 270 | 270 | 540 |
| (Days 15, 71, 127) | (Days 15, 71, 127) | ≥ 40 to < 60 | 0 | 0 | 300 | 300 | 600 |
| | | \geq 60 to < 100 | 0 | 0 | 330 | 330 | 660 |
| | | ≥ 100 | 0 | 0 | 360 | 360 | 720 |
| Open-Label Blinded loading | \geq 30 to < 40 | 1200 | 120 | 0 | 120 | 240 | |
| Extension (10 mg/mL | dose (Day 183) | ≥ 40 to < 60 | 2400 | 240 | 0 | 240 | 480 |
| formulation) | (24) 100) | ≥ 60 to < 100 | 2700 | 270 | 0 | 270 | 540 |
| | | ≥ 100 | 3000 | 300 | 0 | 300 | 600 |
| Open-Label | Open-Label Open-label | \geq 30 to < 40 | 2700 | 27 | 0 | 27 | 54 |
| Extension (100 mg/mL formulation) maintenance dose (Days 197 to 1037, q8w) | ≥ 40 to < 60 | 3000 | 30 | 0 | 30 | 60 | |
| | , 3 | ≥ 60 to < 100 | 3300 | 33 | 0 | 33 | 66 |
| | | ≥ 100 | 3600 | 36 | 0 | 36 | 72 |

a Dose regimen will be based on the participant's most recently recorded body weight. Contact the Alexion Medical Monitor or designee if a participant's weight drops below 30 kg during the Randomized Controlled Period or Open-Label Extension Period.
 Abbreviation: q8w = every 8 weeks

Table 13: Reference Chart for Weight-based Dosing – Study Part B

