6.6. Dose Modification

Dose modification is not permitted for this study. However, in the event of a missed or incomplete dose, and with the guidance of the Sponsor, unscheduled doses may be administered in order to limit the risk of losing complete terminal complement inhibition.

In the event of treatment discontinuation during the Randomized Controlled Period modifications to the first dose of the OLE may be required (see Section 6.5.3).

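### Protocol 6.5.3 gives two different first OLE doses to ravulizumab participants who stop after Week 18 (Part A) or Week 42 (Part B) following acute therapy

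*Protocol*

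**What the plan says.** All of the following is in the Protocol.

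- **6.5.3, general sentence.** It is addressed to every participant, in either arm, who received acute therapy during the RCP and may go on. Those who "are permitted to enter the OLE will require a weight-based blinded loading dose at Week 26 (Part A) or Week 50 (Part B"). It refers to Tables 12 and 13 and to Section 6.1.1.
- **6.5.3, early stoppers on ravulizumab.** "Participants in Part A who discontinue therapy before Week 18 will resume treatment in Week 26" with the loading dose in the Placebo Group section of Table 12. Part B has the parallel rule for stops before Week 42.
- **6.5.3, late stoppers on ravulizumab.** Part A participants who stop after Week 18 "will resume treatment in Week 26 with the weight-based blinded dose described in the Ravulizumab Group section of Table 12". Part B participants who stop after Week 42 "will resume treatment in Week 50 with the weight-based blinded dose described in the Ravulizumab Group section of Table 13".
- **6.1.1.** The regimen "consists of an initial loading dose at the beginning of the Randomized Controlled Period and the OLE followed by maintenance dosing", with no distinction between arms.
- **6.1.1.1, 6.1.1.2 and 6.3.2.** The ravulizumab group receives a blinded 900 mg at Week 26 or Week 50, and the placebo group receives the loading dose.
- **6.6.** After a stop during the RCP, "modifications to the first dose of the OLE may be required (see Section 6.5.3").

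**The concern.** A ravulizumab participant who has confirmed Clinical Worsening, receives acute therapy, stops study drug after the Week 18 or Week 42 visit and enters the OLE falls under both the general sentence and the late-stopper sentence. The first requires a loading dose. The second points to a row that is not a loading dose. Both cannot be followed at the same infusion.

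At stake is the dose actually given at Week 26 or Week 50. With it go exposure in the first weeks of the OLE and the peak PK/PD sample drawn after that infusion. If sites resolve the conflict differently, OLE exposure and PK/PD summaries would mix two regimens in this subset, with no protocol rule to say which was intended.

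**Working it through.** The plan states no statistical figure on this point. The check compares the text with the dose tables.

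**1. What each instruction means in mg.** The inputs are the Day 183 rows of Table 12 (10 mg/mL) and the Day 351 rows of Table 13 (100 mg/mL). Dose = volume × concentration.

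- Ravulizumab Group: 90 mL × 10 = 900 mg (Table 12) and 9 mL × 100 = 900 mg (Table 13), in all four bands.
- Placebo Group: 120, 240, 270 and 300 mL × 10 = 1200, 2400, 2700 and 3000 mg. Table 13 gives 12, 24, 27 and 30 mL × 100, the same doses.

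For the 60 to under 100 kg band, Table 12 has "≥ 60 to < 100 | 900 | 90 | 180 | 270 | 540" in the Ravulizumab Group and "≥ 60 to < 100 | 2700 | 270 | 0 | 270 | 540" in the Placebo Group. Only the Placebo Group rows are labelled as a loading dose on that day, and their values match the loading doses in Table 11.

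| Weight band (kg) | General sentence (mg) | Late-stopper sentence (mg) | Gap (mg) | Ratio |
|---|---|---|---|---|
| 30 to <40 | 1200 | 900 | 300 | 1.33 |
| 40 to <60 | 2400 | 900 | 1500 | 2.67 |
| 60 to <100 | 2700 | 900 | 1800 | 3.00 |
| 100 or more | 3000 | 900 | 2100 | 3.33 |

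**2. Can the case occur?** Yes. Section 4.1.3 rechecks the worsening criteria 4 weeks (± 7 days) after they are first met. Criteria first met at Week 18 are confirmed at 18 + 4 = Week 22 (Weeks 21 to 23). In Part B, criteria first met at Week 42 are confirmed at about Week 46. Acute therapy and the stop then come after the Week 18 or Week 42 visit, and 6.5.3 permits OLE entry.

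**3. Does another section settle it?** No. Section 6.1.1, which the general sentence cites, describes a loading dose at the start of the OLE without separating arms, and so supports the general sentence. Sections 6.1.1.1, 6.1.1.2 and 6.3.2 give the ravulizumab group 900 mg, and so support the late-stopper sentences. Section 6.6 sends the reader back to 6.5.3.

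**4. The boundary.** The timed sentences cover stops before and after Week 18 or 42. A stop at that visit is in neither, and only the general sentence reaches it. This can also happen: criteria first met at an unscheduled visit near Week 14 may be confirmed at the Week 18 visit. Infusion comes last at each visit, so such a stop could fall before or after that day's dose.

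**5. What lies downstream.** Sections 6.1.1.1 and 6.1.1.2 end the RCP once the predose assessments at Week 26 or 50 are complete, so the disputed infusion comes after the TIS40 assessment. Tables 1 and 2 assign the trough sample of that day to the RCP and the peak sample to the extension.

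**The case against.** The best defence is that the general sentence is only a lead-in. Rules by arm and stopping time follow it directly, and the specific should govern the general. If the general sentence governed, the late-stopper sentences would have no effect. Section 6.6 says that a changed first dose may be required, which fits a rule for some stoppers and not others. Under 4.1.4, a participant who received the Week 18 or 42 dose has completed RCP treatment, which suggests a dividing line. In practice, central allocation through IRT, the unblinded pharmacist in Part B or the Pharmacy Manual may already fix the dose.

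This shows a plausible intent, and it stands to that extent. It does not remove the contradiction. The general sentence is universal and mandatory, has no exception, and cites a section that itself speaks of a loading dose at the start of the OLE. Nor can the sentences be separated by reason for stopping: the late-stopper sentences carry no such limit and sit in the section on acute therapy. Section 6.5.3 does not use the 4.1.4 criterion. The Pharmacy Manual was not available, and even a clear manual would leave the protocol inconsistent.

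Three stronger readings are tempting, and the documents do not support them.

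- A reader might infer that a loading dose given here is a reportable overdose under Section 8.4. That section refers to doses above what the protocol specifies, and a loading dose given under the general sentence is specified by the protocol.
- A reader might see a weak dosing check in the equal total volumes (240, 480, 540 and 600 mL in both groups of Table 12). Equal volumes are what the blind needs.
- A reader might fault the description of 900 mg as weight-based. The placebo, diluent and total volumes in those rows do vary by weight band, so the phrase is defensible.

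**Conclusion.** The contradiction is real and should be fixed. Section 6.5.3 gives one group of participants two incompatible doses, 300 to 2100 mg apart (1.33 to 3.33 times), and nothing elsewhere in the protocol resolves it.

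Its reach is narrow. Only ravulizumab participants with confirmed Clinical Worsening, acute therapy, a stop in the last 8 weeks of the RCP and OLE entry are affected, together with the boundary case. The planned ravulizumab arms of 24 (Part A) and 76 (Part B) are ceilings. The documents give no rate for these events, so the number is unknown, though it should be small.

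A reader might infer that the primary result is at risk. It is not: TIS40 is assessed before the infusion in question. The consequences are confined to Week 26/50 dosing, early OLE exposure and the peak PK/PD sample. The conclusion assumes that discontinuing therapy in the timed sentences means stopping study drug. It takes no position on which dose is correct.

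**What to change.** In Section 6.5.3, reconcile the general loading-dose sentence with the two late-stopper sentences so that each participant has one Week 26 or Week 50 instruction. Bring the Section 6.1.1 wording on the start of the OLE into line with the result. State which rule covers a stop at the Week 18 or Week 42 visit itself, including whether it matters that the dose was given that day. The sponsor decides the clinical rule.

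The cost is wording in 6.5.3 and 6.1.1 and a check that the Pharmacy Manual agrees. No new data and no change to the TIS40 analysis are needed.

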6.6. Dose Modification

Dose modification is not permitted for this study. However, in the event of a missed or incomplete dose, and with the guidance of the Sponsor, unscheduled doses may be administered in order to limit the risk of losing complete terminal complement inhibition.

In the event of treatment discontinuation during the Randomized Controlled Period modifications to the first dose of the OLE may be required (see Section 6.5.3).

